15.1.2 Definition of Serious Adverse Events

A SAE is any untoward medical occurrence in a patient or clinical trial patient administered a medicinal product which does not necessarily have a causal relationship with this treatment. A SAE can therefore be any unfavorable and unintended sign (including an abnormal laboratory finding), symptom, or disease temporally associated with the use of an investigational product, whether or not related to the investigational product and resulting in:

- Death.
- Life-threatening.
- In-patient hospitalization or prolongation of existing hospitalization.
- Persistent or significant disability/incapacity.
- Congenital anomaly/birth defect.

Other event(s) considered important medical event.

Examples of other events which could be considered medically important and reported as serious are: intensive treatment in an emergency room or at home for allergic bronchospasm; blood dyscrasias or convulsions that do not result in hospitalization; or development of drug dependency or drug abuse.

Clarifications:

- "Occurring at any dose" does not imply that the patient is receiving investigational product.
- Life-threatening means that the patient was, in the view of the Investigator, at immediate
 risk of death from the event as it occurred. This definition does not include an event that,
 had it occurred in a more severe form, might have caused death.
- Hospitalization for elective treatment of a pre-existing condition that did not worsen during the study is not considered an SAE.
- Complications that occur during hospitalization are AEs. If a complication prolongs hospitalization, the event is a SAE.
- "In-patient" hospitalization means the patient has been formally admitted to a hospital for medical reasons. This may or may not be overnight. It does not include presentation at a casualty or emergency room.
- With regard to important medical events, medical and scientific judgement should be used in deciding whether prompt reporting is appropriate in this situation.

An unexpected adverse event is an AE whose nature, severity or outcome is not consistent with the information given into the reference document as defined in the study protocol.

Expected serious adverse reactions should be considered always unexpected if:

- ➤ have an unexpected outcome (e.g., a fatal outcome).
- > have an increase in the rate of occurrence, which is judged to be clinically important.

Expectedness evaluation is performed by the Sponsor based on Reference Safety Information (RSI).

15.1.8 Prompt Reporting of SAE to the Sponsor

Any serious adverse event occurring during the study, once the Investigator determines that the event(s) meet the protocol definition of a SAE, regardless whether related or not to the investigational drug, must be reported immediately (i.e. within 24 hours) to the Sponsor (or its designee).

Information about all SAEs will be reported using the SAE tool of the eCRF. In case of technical difficulties, SAE notification can be carried out filling paper SAE Report form and it must be mailed or faxed using the following contact details:

One "SAE Report form" should be used for each SAE. However, if at the time of initial reporting, multiple SAEs are present that are temporally and/or clinically related, they may be reported on the same "SAE form" preferably as a diagnosis.

The SAE form must be written in easily readable reading way. It must be completed as thoroughly as possible with all available details of the event, signed by the Investigator (or appropriately qualified designee), and reported immediately to the Sponsor (within 24 hours from first awareness of the event).

If the Investigator does not have all information regarding the event, he/she will not wait to receive additional information before compiling the form and notifying the event to the Sponsor, although the following minimal information is required:

The following minimal information is required as initial report:

- Name, affiliation, telephone and fax number of the reporting Investigator
- Investigational product(s)
- Study code
- Study Centre number
- Patient identification number, sex and age (years)
- Last investigational drug administration
- Description of the adverse event,
- Measures taken if any
- Causal relationship by the investigator

The Investigator will always provide his/her assessment of causality at the time of the initial report.

The additional information as soon as available will be recorded in a separate SAE form completed in every part that will be sent as a follow-up report.

If follow-up information obtained subsequently leads the investigator to change the assessment of causality, the SAE form may be appropriately amended, signed and dated, and resubmitted to the Sponsor as follow up report.

SAEs will be followed-up until resolution or the patient is lost to follow up. SAEs still present at the end of the study period and for the subsequent 30 days, must be followed until an outcome is determined or the patient is lost to follow up.

If a patient dies during participation in the study or during a recognized follow-up period, the Investigator should send to the Sponsor, together with SAE Form, any other available post-mortem information, including autopsy and histopathology.

The Sponsor must be informed of any code breaking (see Section 11.5 Unblinding of randomization

in case of emergency).

In accordance with local IEC requirements, the Investigator must also notify IEC of any SAEs according the guidelines of the Ethics Committee.

15.1.9 Regulatory Reporting Requirements for SAEs

The Sponsor has a legal responsibility to notify both the local regulatory authority and other regulatory agencies about the safety of a drug under clinical investigation.

Prompt notification of SAEs by the Investigator to the appropriate project contact for SAE receipt is essential so that legal obligations and ethical responsibilities towards the safety of other patients are met.

The Investigator must promptly report all SAEs to the Sponsor or his designee, in accordance with the procedures detailed in section 15.1.8 Prompt Reporting of SAE to the Sponsor.

The Investigator, or responsible person according to local requirements, must comply with the applicable local regulatory requirements related to the reporting of SAEs to regulatory authorities and the IEC.

15.1.10 Post study AEs and SAEs

A post-study AE/SAE is defined as any event that occurs outside the AE/SAE detection period as defined previously.

Investigators are not obliged to actively seek AEs or SAEs after the clinical study termination. However, if the Investigator becomes aware of any SAE, including death, at any time after a patient has been discharged from the study and he/she considers the event reasonably related to the Investigational Product, the Investigator should promptly notify the Sponsor, according to the process explained in section 15.1.8 Prompt Reporting of SAE to the Sponsor.

Serious and non-serious AEs will be recorded from the ICF signature to the Final/Early Termination Visit regardless of whether the participant is on treatment.

SAEs will be recorded and reported as appropriate and followed-up until resolution or stabilization. Non-serious AEs will be recorded as appropriate and followed-up until Final/Early Termination Visit.

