- b. If the subject cannot go back to the clinical site for one or more of the following visits: Visit 5, 7, 9 and 10 or ETV, they can be performed at the subject's home.

- Dose to be taken under observation at each scheduled visit at the clinical center. The exact time of dose administration should be recorded at all visits.
- I. If the subject cannot go back to the clinical center for Visit 5, 7, 9 or ETV, the empty packs and the unused investigational product of the relevant period will be collected by the study nurse during the home visit.

- n. The final 2 week follow up period are considered also as final 2 week wash out period for the 4th treatment period.
- o. In case, during a treatment period or during a washout period, a subject should experience an exacerbation of the CIPO related gastrointestinal symptoms that is not controlled by permitted medications and is not judged as an adverse event, he/she will attend an early switch visit (ESV) at the site. After being reassessed, he/she will start the next scheduled treatment period (SOT-2 or SOT-3 or SOT-4), without completing the ongoing treatment or washout period. ESV will be Day 1 of the relevant period (SOT-2 or SOT-3 or SOT-4) based on the timing of early switch. Only one early switch is allowed during the study.

TABLE OF CONTENTS

	LIST OF ABBREVIATIONS AND DEFINITION OF TERMS	
2		
	.2 ETHICAL CONDUCT OF THE STUDY	
	.3 SUBJECT INFORMATION AND CONSENT	
3	GENERAL INFORMATION	29
4	BACKGROUND AND RATIONALE	
5	STUDY OBJECTIVES AND ENDPOINTS	
	.1 PRIMARY STUDY OBJECTIVE AND ENDPOINT	33
6	OVERALL STUDY DESIGN AND PLAN	36
7	DISCUSSION OF STUDY DESIGN, INCLUDING THE CHOICE OF CONTROL GROUPS	
8	BENEFIT-RISK EVALUATION	
9	SELECTION OF STUDY POPULATION	40
(.1 Number of Participants	40
(.2 Inclusion Criteria	40
(1.3 Exclusion Criteria	41
(.4 PREMATURE DISCONTINUATION FROM THE STUDY PER SUBJECT	42
10	TREATMENTS	43
	0.1 Treatments to be Administered	43
	0.2 Investigational Products	44
	10.2.1 Test preparation	44

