7 DISCUSSION OF STUDY DESIGN, INCLUDING THE CHOICE OF CONTROL GROUPS

This study will evaluate the safety, tolerability and efficacy of velusetrag 15 mg once a day versus placebo, in improving the symptoms severity associated with CIPO, in subjects with idiopathic CIPO and CIPO secondary to neurodegenerative conditions (e.g., Parkinsonian Syndromes, etc.).

CIPO is a chronic, rare disease, with fluctuating symptoms and differences in underlying pathology, which may respond differently to active treatment. Therefore, a standard parallel group placebo-controlled study may not allow to detect clear benefit due to the large variability of clinical presentation.

A n=1 cross over, placebo-controlled study design, as the one chosen for the present study, allows to assess the treatment effect in every subject, thereby allowing individual subjects to act as their own control and evidencing a positive effect even in a single subject, avoiding under-estimation of the therapeutic efficacy (Emmanuel, 2012).

Subjects will be evaluated over a total of 16 weeks, receiving either velusetrag 15 mg or placebo, once daily, for four randomized periods of 4 weeks each. The planned treatment time period is considered enough to demonstrate a difference between active treatment and placebo. The washout periods' duration has been selected based on velusetrag and active metabolite half-life.

Efficacy will be assessed after each 4 weeks of treatment for primary analysis. The choice of placebo as comparator will allow for estimation of the real treatment effect of velusetrag and is considered acceptable due to: i) the lack of any approved treatment for CIPO; ii) the fact that symptomatic rescue therapies are allowed, and iii) the close monitoring during a relatively short treatment period. Moreover, participants, that during the study should experience significant exacerbation of CIPO-related gastrointestinal symptoms that are not controlled by permitted medications and are not judged as adverse events, after being reassessed may decide to continue the study and start the subsequent treatment period, or discontinue the study.

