9.4 PREMATURE DISCONTINUATION FROM THE STUDY PER SUBJECT

Any subject (or his/her legally authorized representative) may withdraw the consent to participate in the study at any time without prejudice. The investigator must withdraw from the study any subject who requests to be withdrawn. A subject's participation in the study may be discontinued at any time at the discretion of the investigator and in accordance with his/her clinical judgment. When possible, the tests and evaluations listed for the ETV should be carried out.

If a subject withdraws before completing the study, the Investigator should determine the primary reason for premature discontinuation of the study, and the reason and date of withdrawal will be recorded on the e-CRF. The Sponsor will be notified of all subject withdrawals.

Reasons for which the investigator or the Sponsor MAY withdraw a subject from the study, or a subject MAY choose to terminate participation before completion of the study include, but are not limited to, the following:

- Treatment failure including the use of and scopolamine, erythromycin and opioids for analgesic use during the study.
- Positive COVID-19 test
- Adverse event: any (significant) adverse event that in the opinion of the investigator, sponsor, or subject is not compatible with study continuation.
- Death.
- Loss to follow-up: the loss or lack of continuation of a subject to follow-up.
- Significant non-compliance with investigational product: an indication that a subject has not agreed with or followed the instructions related to the study medication.

- Physician or sponsor's decision: any other reason that in the opinion of the Investigator or Sponsor may affect the safe participation of a subject in the trial or significantly jeopardize the study design.
- Subject's withdrawal of the informed consent: study discontinuation requested by a subject for whatever reason.
- Significant protocol violation.
- Other: different than the ones previously specified.

In case of premature study discontinuation, a final evaluation should be completed at the time of discontinuation as per section 11.2.7 Early Termination Visit (ETV), when applicable. Subjects who discontinue treatment due to SAE will be followed up until the event resolves or stabilizes.

Subjects withdrawn from the study will not be replaced. The data of subjects who are withdrawn will be considered for evaluation.

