11.2.7 Early Termination Visit (ETV)

The following procedures/assessments will be completed during the ETV. if the subject agrees to perform the visit and can attend the visit at the clinical center:

6. Blood collection (in fasting condition):

- 13. Review and record any AEs that occurred since the previous visit.
- 14.
- 15. Review the e-diary to assess the completeness. Weekly questionnaires will be completed during the ETV.
- 16. Collect all investigational product bottles and account investigational product.

Home visit: In case the subject cannot attend the visit at the clinical center, this visit can be scheduled at home and a home nursing service will perform the visit. The clinical staff at the study center may attend the visit remotely. The data collected (source documents) during the home visits by the nurse will be transmitted on the same day to the clinical center in order to allow the study doctor to perform a preliminary clinical evaluation regarding safety. In case of home visit the same procedures scheduled for the visit at the clinical center will be performed with the exception of physical examination that will not be performed.

The nurse will collect the empty packs and the unused investigational product of the relevant period during the ETV.

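### Subjects who stop early have no scheduled collection of new AEs, and no follow-up of non-serious AEs, after an Early Termination Visit held at discontinuation; completers are observed for about 15 days after the last dose.

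*Protocol*

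**What the plan says.** **Recording window.** Protocol 15.1.10: "Serious and non-serious AEs will be recorded from the ICF signature to the Final/Early Termination Visit", on or off treatment. For events that are not serious, the same section adds: "Non-serious AEs will be recorded as appropriate and followed-up until Final/Early Termination Visit".

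**Timing of the early visit.** Protocol 9.4: "a final evaluation should be completed at the time of discontinuation as per section 11.2.7 Early Termination Visit (ETV), when applicable". Section 11.2.7 makes the visit conditional: "if the subject agrees to perform the visit and can attend the visit at the clinical center", with a home visit as the alternative. AEs since the previous visit are recorded there. The readable ETV steps end with return of study medication, whereas the end-of-treatment visits in 11.2.3 and 11.2.5 end by booking the next visit.

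**Completers.** The last dose of period 4 is taken at Visit 9 (Day 154 ± 1, section 11.2.5). AEs are reviewed again at End of Follow-up (Day 169 ± 1, section 11.2.6). Footnote n of the Schedule of Assessments treats this interval as a wash-out: "The final 2 week follow up period are considered also as final 2 week wash out period for the 4th treatment period". Section 7 gives the basis for the wash-out length: "duration has been selected based on velusetrag and active metabolite half-life".

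**Provisions beyond the ETV.** Section 9.4 follows subjects who stop because of an SAE until it resolves or stabilises. Sections 15.1.8 and 15.1.10 follow SAEs generally to resolution, stabilisation or loss to follow-up. Section 15.1.8 also has a clause on SAEs present at study end and over the next 30 days. Section 15.1.10 requires an SAE judged reasonably related to be reported if the investigator learns of it after discharge, but places no duty to look for events after the study has ended.

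**Analysis.** Under Protocol 16.3.4 and SAP 6.4.3, any AE starting on or after first intake is treatment-emergent and is assigned to the last treatment taken. Neither gives an end date. SAP 4.4.3 keeps discontinued subjects in the safety analysis.

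**The concern.** The plan itself treats off-drug time as relevant to safety. Section 15.1.1 counts events in wash-out and follow-up as AEs, and every completed period is followed by about 2 weeks in which they are recorded. A subject who stops on drug loses that interval. Leaving because of an AE is one of the listed reasons in 9.4, so those affected include the subjects most likely to have had a tolerability problem.

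Three things are at stake. New events after the last dose may go unrecorded. The outcome of a non-serious AE that caused the stop may stay unknown. And because TEAEs are assigned to the last treatment taken, a completed period carries 4 weeks on drug plus its wash-out, while a period cut short by an on-drug ETV carries nothing after the stop. No adjustment for this unequal observation is visible. With 16 subjects and no data monitoring committee (section 18.4), each lost event matters.

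**Working it through.** **1. Off-drug observation for completers.** The plan states 2 weeks (section 6). Inputs: Visit 9 on Day 154 ± 1, End of Follow-up on Day 169 ± 1.

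- Nominal: 169 − 154 = 15 days.
- Shortest: 168 − 155 = 13 days.
- Longest: 170 − 153 = 17 days.

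This agrees with the stated 2 weeks.

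**2. The same interval after earlier periods.** Nominal visit days from the Schedule of Assessments, last dose to next start of treatment:

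- Period 1: 43 − 28 = 15 days.
- Period 2: 85 − 70 = 15 days.
- Period 3: 127 − 112 = 15 days.

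So every period completed without an early switch has about 15 days in which new AEs are still collected.

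**3. Off-drug observation for early stoppers.** No section sets an interval between last dose and ETV; section 9.4 says only that the evaluation is made when the subject discontinues.

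- Stop on drug, ETV on the day of the last dose: 0 days. This is the minimum, and it assumes the two coincide.
- Stop during a wash-out: the days already elapsed since the last dose, up to about 15.

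The shortfall against completers is therefore between 0 and about 15 days per subject.

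**4. What continues after the ETV, by type of event.**

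| Event | After the ETV |
|---|---|
| SAE already known | Followed to resolution, stabilisation or loss to follow-up (9.4, 15.1.8, 15.1.10) |
| New SAE | Reported if the investigator learns of it and judges it related (15.1.10); whether the 30-day clause in 15.1.8 adds active collection is unclear |
| Non-serious AE already known, including one that led to stopping | No follow-up (15.1.10) |
| New non-serious AE | Not collected (15.1.10) |

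**5. How many subjects.** The only planning figure is the 25% allowance for dropouts and missing pairs in section 16.1.

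- Pairs lost: 0.25 × 32 = 8, which reproduces the planned 32 − 8 = 24 pairs.
- Every lost pair due to missing data and none to withdrawal: 0 subjects.
- Every withdrawal loses both pairs: 8 / 2 = 4 subjects.
- Every withdrawal loses only the second-cycle pair: 8 / 1 = 8 subjects.

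The illustrative range is 0 to 8 of 16. It does not predict on-drug stops, since some withdrawals would fall in a wash-out.

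**The case against.** The strongest reply is that early stoppers are not abandoned. Known SAEs are followed past the ETV, and related SAEs that come to light after discharge are reported. This stands. A reader might infer that subjects who stop because of harm get no post-dose safety follow-up at all; sections 9.4, 15.1.8 and 15.1.10 contradict that. The gap concerns new events and non-serious events.

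Second, the text is incomplete. Section 15.1.10 refers back to an earlier definition of the detection period, and sections 15.1.3 to 15.1.7 are not in the readable text; most ETV items are also blank. A longer window could be defined there. This lowers confidence but does not remove the point: 15.1.10 states its own end point, and a longer window elsewhere would conflict with it. Also, its release from active searching refers to the end of the clinical study, which is not plainly one subject's early exit.

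Third, the harm is inferred. A reader might conclude that drug is still present after the ETV, or that velusetrag's TEAE rate is understated. The documents support neither as fact. No half-life is given; section 7 says only that half-life guided the wash-out length. The direction of any bias depends on which treatment causes more on-drug stops, which is unknown. Section 8 reports that gastrointestinal AEs in the constipation study typically began and resolved within 1 to 2 days of starting treatment, so late new events of that kind may be few. Subjects leaving in periods 2 to 4 will usually have had an earlier wash-out under observation. All of this limits the likely size; none of it supplies the missing outcome of an AE that caused the stop.

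Fourth, SAP 1.1 (version 2.0, May 2023) describes randomisation in the past tense, so an amendment may reach few subjects or none. That is a fair limit on its benefit.

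**Conclusion.** The point holds in this limited form. After an ETV held at discontinuation, the readable protocol schedules no collection of new AEs and no follow-up of non-serious AEs, while completers are observed for about 15 days off drug. This follows from rules the protocol states, not from missing detail. For a subject who stops on drug the off-drug observation can be 0 days; for one who stops in a wash-out the shortfall is smaller.

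The effect on TEAE incidence cannot be sized from the documents. It would fall more on whichever treatment causes more on-drug stops. The count of 0 to 8 subjects rests on reading the 25% allowance as withdrawals to differing degrees, and is for scale only. Confidence is medium because of the unavailable sections. The change is worth making because it is cheap and gives early stoppers the observation window completers already have.

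**What to change.** In Protocol 15.1.10, 9.4 and 11.2.7, run AE and SAE collection to the later of the ETV and 2 weeks after the last dose. Follow any AE that led to discontinuation to the end of that window. Close it with one telephone contact by existing site staff. Exempt subjects who refuse further contact.

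In the same amendment, reconcile the new window with the 30-day clause in 15.1.8, stating whether new SAEs in those 30 days are collected, and with the detection period that 15.1.10 says was defined earlier.

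The cost is a short amendment and one call per early stopper, with the last-contact date up to 2 weeks later for those subjects. No dose, stopping rule or efficacy analysis changes. If no subject is still under observation, the remaining step is to report, by treatment, the days from last intake to last AE assessment for early stoppers, using dates already collected.
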